4.4 END OF STUDY DEFINITION

A participant is considered to have completed the study if he or she has completed the online survey questionnaire that is emailed on Week 8, as shown in the Schedule of Activities (SoA), Section 1.3. The end of the study is defined as 66 days after the last participant is enrolled or when that participant completes the Week 8 survey questionnaire, whichever is sooner.

5 STUDY POPULATION

5.1 INCLUSION CRITERIA

In order to be eligible to participate in this study, an individual must meet all of the following criteria:

1. have chronic pain, from any underlying condition, using as examples but not limited to the administrative definition of ICD-10 code series G89.X or one or more of 134 chronic overlapping pain condition codes, as previously standardized and validated by an expert panel (see Tables 2 and 3)
2. have experienced average pain intensity of >3 out of 10 within the previous week;
3. are >13 years of age;
4. are able to read/write English;
5. have either a personal computer, tablet, or smartphone;
6. live in a designated rural zip code as defined by the Federal Office of Rural Health Policy (FORHP) data (RUCA Codes 4-10).

5.2 EXCLUSION CRITERIA

An individual who meets any of the following criteria will be excluded from participation in this study:

1. have a condition that interferes with use of the intervention (e.g., significant visual or auditory impairment, any history of seizure);
2. are hospitalized;
3. are receiving active cancer treatment;
4. are receiving end-of-life care;
5. have cognitive impairment that affects participation.
6. have previously used the EaseVRx+ or painTRAINER programs

We will collect data on key patient characteristics, including type of pain condition, sex, age, race, ethnicity, State and zip code, Rural-Urban Commuting Area (RUCA) codes (a composite measure of population density, urbanization, and daily commuting), pain severity, opioid use, comorbidities, social support, and COVID-19 impacts (unemployment, financial hardship, family or personal COVID-19 diagnosis).

5.3 LIFESTYLE CONSIDERATIONS

Women who are currently pregnant or planning to become pregnant will not be excluded from the study

5.5 STRATEGIES FOR RECRUITMENT AND RETENTION

The target sample size is 300. The population impacted by this research broadly encompasses individuals with many different types of chronic pain conditions, including somatic, musculoskeletal, neuropathic, and visceral pain. Using data from the Federal Office of Rural Health Policy (FORHP), rural Louisiana has a high prevalence of nearly 32% non-Hispanic Black, rural California has 2.5%, and Alabama 22.7%. We will oversample with a target of 20% for non-Hispanic Blacks in this study. We will have a monitoring plan to ensure that we maintain our 20% goal throughout conduct of the study. Rural California is 30% Hispanic, while Alabama and Louisiana have fewer than 2% Hispanic rural populations. The mean across states is 11.2%. The national mean of rural Hispanic populations is 6.6%. Because we will likely receive more patients from Alabama and Louisiana than from California (because there are two sites in the Deep South vs. one in urban California), we anticipate a weighted mean of closer to 8% Hispanic and will therefore target this value for our study.

All four clinical sites have patient cohort search engines that will be used to identify patients with chronic pain. The informatics department at each site will pull zip code data for each potential participant, which will be matched with year 2010 RUCA zip codes provided by the USDA. This will provide a list of all possible participants that meet our desired criteria. We will monitor enrollment monthly and use the list to enrich enrollment as needed throughout the study to maintain the 20% target for the overall sample (across all three States).

Across the four recruitment sites (Cedars-Sinai, Ochsner, UAB, Bendcare) over 10,000 patients are designated as being in a rural area. Though all four sites are based in urban location. There is a significant amount of rural area surrounding each area. Note that [name] from University of Alabama is associated with Bendcare and the UAB coordinator will serve the same role for patients identified from Bendcare.

Recruitment for the proposed trial will be maximized using several strategies:

- Patients will be screened over a period of 24 months. Due to the COVID-19 pandemic, remote recruitment, which we have implemented and proved to be effective in our previous VR trials, will supplement in-person recruitment to ensure that we can reach the target enrollment goal.

- Identification: The prospective participants will be identified through existing registries, provider recommendation, and via automated EHR review using queries / clinical trial search programs / cohort builders (e.g. Deep6, Slicer Dicer, i2b2) at partner sites.
- Recruitment: No in-person visits are required to be recruited for this trial.
 - Main Method: All eligible participants with a valid email in the medical record will be contacted by a research coordinator by email and patient-portal using an IRB approved recruitment letter to explain the study. An informational brochure will be attached to the email communication.
 - Alternative Method: If no valid email is available but a phone number is available, the study coordinator will contact the potential participant by phone to explain the study. At that time, the coordinator will also collect the potential participant's email (if available and the potential subject expresses interest in receiving additional information via email). An informational brochure will be attached to a future email communication.
- Justification for the alternate method: Our study was funded to address healthcare disparities for underserved and vulnerable populations (rural participants, in this case), and we are concerned that our study is excluding individuals who would otherwise qualify but have inadequate contact information on their chart, to the detriment of the study. For example, our inclusion criteria specifically target populations who are unlikely to be in close proximity to the participating academic health systems, and this condition naturally hinders opportunity to collect some/all personal information due to the infrequency of these (often all-day when travel time is included) visits. Especially with this specific study, the recruitment letter requirement may be biasing our study sample to reflect a population of higher tech literacy, closer proximity to the health center, etc. Further, we are underperforming the recruitment targets of Black and Hispanic individuals set by our NINR project officer, and all sites have patients from these cohorts without valid email addresses.
- All patients will be able to opt-out of the study via email or by phone. We request removal of an official wait time between sending the email/letter and contacting subjects by phone. Our justification is that, to date, in the rural chronic pain study alone, 153 recruitment letters have been sent to Cedars-Sinai patients. However, none of them have contacted our study staff prior to the 7-day period, and of the 33 individuals who were sent a recruitment letter and later declined, only two declined by email. 98.7% of recruitment letters have not obviated the need for a follow-up recruitment call, and this response rate compares to our other trials. Most individuals do not recall seeing or reading the letter when finally reached by phone.
- If contacting a patient by phone, study coordinators will ensure the identity of the person on the phone call is indeed the prospective participant that was intended to be called.
- Consent: An IRB-approved script will explain the purposes, procedures, and potential risks of the study and rights as research participants. REDCap will be used to email the IRB approved electronic consent form to the patient. Participants will have the opportunity to carefully review the electronic consent form and ask questions prior to signing. Study staff may reach out to participants who have been sent a consent form but have not yet signed to assist with the

eConsent process or record a reason for withdrawn interest, as long as the participant has not indicated a reason for not signing the form. Participants will complete their consent forms electronically using the 21 CFR 11-compliant online REDCap platform. The informed consent will be signed by the patient and the designated investigator before the participant undergoes any study-specific procedures. The rights and welfare of the participants will be protected by emphasizing to them that the quality of their medical care will not be adversely affected if they decline to participate in this study.

- **Post-Consent:** A copy of the informed consent documents will be provided to the participants for their records via email, and via postal service if no email is available. Participants will consent remotely and those randomized to the VR arm will receive their study equipment through a secure FedEx package. Study participants will receive their study equipment or documentation through secure FedEx package delivery. Retention to the 12-week study will be managed using protocolized reminder calls, emails, and/or SMS text messages to complete the study surveys. Study coordinators will contact the participant following non-completion of a survey if >1 week has elapsed since the initial survey send date. The study coordinator will employ a Tableau dashboard that provides protocol adherence data to guide contact decisions.
- Participants who complete the consent form will be required to finish the baseline questionnaires in order to be randomized and have the study equipment shipped to them as described above. Participants will be emailed tracking information and, if randomized into the VR arm, videos describing use of the intervention.
- Participants will be called for study onboarding once the VR device or painTRAINER workbook is delivered to their home. During this call, patients will be asked if they reviewed the startup instructions that were provided in the intervention tracking information email, and coordinators will answer any remaining questions and guide participants through the device or program if necessary. If participants are unreachable by phone, study staff will seek to schedule a phone call or confirm the participant's understanding of study procedure by email, or by patient prior to initiation of study surveys. Contact information will be provided for technical support throughout the participant's study enrollment.

This protocol is not high risk for subject attrition; the intervention itself is considered low risk by our IRB.

Strategies for retention include the following:

- During the recruitment process, subjects will be educated about the importance of their role in contributing to research, to increase the likelihood that they will complete the patient reported outcome measures even if they stop using the intervention.
- Participants will be educated on how to use PainTRAINER or VR via educational videos, talking with study staff, and referring to any applicable documentation.
- The subject burden is low. Several data will be acquired passively, through patients using the PainTRAINER (2D mHealth intervention) or EaseVRx (3D VR intervention). There are no visits to their medical provider required by the research protocol.
- Subjects will be compensated for participation in this study (see budget).
- Retention to the 12-week study will be managed using three 24hr reminder emails, phone calls, or SMS text messages, as preferred by the patient, to complete PRO measures. Study coordinators will contact the participant following non-completion of a survey if >1 week has elapsed since the

initial survey send date. The study coordinator will have a dashboard that provides compliance information to the individual patient using a program called tableau (Mountain View, California).

- Participants may be contacted to facilitate study onboarding and survey compliance by their recruiting site study team via patient-portal when allowed by local IRB policy.
- Participants in the VR arm will be required to return the device after completing the surveys on the 8th week to be eligible for the honorarium.

As health services researchers working in highly diverse populations, we recognize that racial and ethnic minorities are underrepresented in clinical research for a wide range of important historical and cultural reasons. We also recognize that there are many strategies that can help overcome barriers and obstacles to participation in clinical trials. Considering the large target populations of Black and Hispanic populations in our rural populations, we will engage in several recruitment strategies designed to increase targeted recruitment, as follows:

- Clarify the agenda behind the research in all written and oral communications.
- Provide clear information about the clinical trial that avoids medical jargon.
- Make recruitment/retention a top priority for research staff.
- Provide regular feedback to referral sources about the status of trial recruitment.
- Speak informally to colleagues to promote protocol awareness and interest.
- Speak at professional and community meetings about trial protocols, and request referrals.
- Highlight our team members who are Black and Hispanic researchers.

6 STUDY INTERVENTION

6.1 STUDY INTERVENTION(S) ADMINISTRATION

6.1.1 STUDY INTERVENTION DESCRIPTION

The two active interventions evaluated in this study are EaseVRx and PainTRAINER. EaseVRx is delivered via a commercially available VR headset. PainTRAINER consists of 2-D visualizations delivered via smartphone or computer.

Skills-Based VR: EaseVRx

EaseVRx was developed by AppliedVR in partnership with pain psychologist [name], Associate Professor of Anesthesiology, Perioperative and Pain Medicine at Stanford University and an NIH- and PCORI-funded investigator in the use of VR for pain management. EaseVRx incorporates the evidence-based principles of CBT, mindful meditation, and physiologic biofeedback therapy using embedded biometric sensors. It combines psychoeducation, pain education, breathing training, relaxation exercises, and executive functioning games to provide a mind-body approach toward living better with chronic pain. The standardized, prescriptive, and reproducible 56-day program delivers a combination of skills training and CBT-related treatments through scheduled daily virtual experiences. The participants are allowed to complete as many sessions as they would like. In addition to the prescribed schedule of content the participant will have access to the full library of content. Each VR experience lasts between 2-16 minutes, with an average duration of 6 minutes. The VR treatment modules are designed to minimize triggers of emotional distress or cybersickness. There are 5 types of modules:

- **Interoceptive:** These modules are designed to help the user understand and perceive what is happening inside the body. They provide a biofeedback-like platform in which the changes in the observed environment reflect a progressively enhanced state of relaxation.
- **Education:** Help the user understand why the VR exercises are relevant to their pain, as well as teaching specific topics often used in pain psychology, including the neurobiology of pain, the role of mood and stress in pain, pain catastrophizing, activity pacing and setting goals. The goal is for the user to create self-management steps and a toolkit of strategies they can use to manage their response to pain.
- **360-degree videos:** High-quality 360 videos with voiceovers, music, and sound effects that are designed to maximize relaxation and engagement of users.
- **Game modules:** Games are designed to maximize distraction and engagement, increasing the cognitive load on patients, and decreasing their perception of pain.
- **Dynamic breathing:** These modules are based on evidence-based biofeedback training designed to enhance awareness of one's physiological response to pain and to self-regulate that response. In a virtual world, the user experiences a gamified biofeedback session in which they are introduced to awareness of their breath via visualization in the form of air bubbles. In multiple sessions, the user receives increasingly challenging tasks to practice diaphragmatic breathing while interacting with the virtual environment. The user is also asked to pace their breath according to an expanding and contracting ring in the environment to slow the breath and create physiological changes associated with relaxation. The user's exhale is measured by the microphone embedded in the headset, offering biodata-enabled immersive therapeutics.

The EaseVRx program has been authorized by the FDA to help with pain reduction in patients 18 years and older diagnosed with chronic lower back pain.

PainTRAINER (2D mHealth intervention)

PainTRAINER is among the most widely-validated mHealth interventions for pain management.⁴⁷⁻⁵⁴ Originally developed by members of our team at Duke and Northwestern University under NIH funding, the app teaches evidence-based pain coping skills using a self-administered, home-based software program. The system delivers eight sessions via any web-connected platform, including Android or iOS smartphones, tablets, or personal computers. The digital curriculum covers progressive muscle relaxation, activity/rest cycling, pleasant activity scheduling, recognizing negative automatic thoughts, pleasant imagery/distraction, problem solving, and monitoring for maintenance. Patients complete one session per week in a pre-determined order. The program can be completed in a flexible manner to accommodate life and medical events. For example, patients can close a session before completing it and later resume where they left off. Training is led by a computerized virtual coach and content is provided in audio to minimize reading and facilitate program completion for sick or low literacy patients. Important information is highlighted on screen with brief, large-font text, with photos, graphics, animations, and interactive exercises to reinforce learning.

[figure not shown]
PainTRAINER includes eight 35-45 minute sessions; each teaches an evidence-based pain coping skill. Users complete one session per week in a predetermined order and can close a session before completing it and later resume where they left off. They can also review completed sessions (e.g., an audio recording of a skill practice, or instructions on how to use a skill). **The program uses an adaptive, mobile responsive mHealth platform:** Users can access it with any Internet-enabled tablet, personal computer, or smartphone. **Smartphone access is important; these devices are increasingly the main platform used to access the Internet, including in underserved populations.** During development of *PainTRAINER*, patients clearly advocated for access to program content and resources through smartphones. Training is led by a

computerized virtual coach who speaks to users. **Content is provided in audio to minimize reading and facilitate program completion for sick or low literacy patients.** Important information is highlighted on screen with brief, large-font text, with photos, graphics, animations, and interactive exercises to reinforce learning. We also added other features to enhance learning and mastery of skills, guided by *social cognitive theory* (e.g., social modeling), *adult learning theory* (e.g., tying skills to personal goals and experiences), *principles of multimedia instruction* (interactive exercises, graphics to reinforce explanations), and *behavior change theory* (e.g., behavior tracking, reminders).

The program includes: (i) the Home Page (customized to users' progress and status by the expert system); (ii) Training Sessions; and (iii) the Expert System (a knowledge database and programmed decision rules or "algorithms" that customize users' experience based on their progress in the program). A login screen takes users to the home page where they access the current week's session, which is highlighted. From there, users access program sessions and features that allow them to manage reminders and goals, log practices, and review progress in easy-to-read graphs. **The interface applies accepted principles of user-centered design to enhance usability in diverse**

populations (e.g., screen layout consistent with major websites; use of audio to minimize reading; simple menus placed predictably on-screen; clear and consistent navigation aids; direct access to important screens and help). **Screen elements are designed for a diverse population** (e.g., easy-to-read type, plain language and audio for low literacy users, images of people from diverse race/ethnic backgrounds). Written content follows federal guidelines for plain language to ensure it is easy to read, understand, and use. The program's back-end database tracks program use meta-data, including sessions experienced, time spent on session, and time of day the session was reviewed. These meta-data allow for secondary "dose-response" analyses. **Figure 1** shows the home page.

Figure 1: PainTRAINER home page

PainTRAINER has been validated in clinical trials, including multiple RCTs. Bennell et al. studied the program in a participant-blinded trial of patients with chronic pain and found greater increases in function, pain coping, and global improvement than a control condition after eight weeks; benefits persisted at 52 weeks and 91% of participants (older adults, **largely from rural, low income areas, consistent with the current study population**) completed all 8 sessions.⁴⁷ Rini et al. found similar results in a controlled trial in patients with painful arthritis that demonstrated improved self-efficacy, reduced anxiety, and less pain-related interference with functioning.⁴⁸ Qualitative research reveals that patients find the program easy to use and are likely to recommend the app to others.⁵⁰ Taken together, research indicates that *PainTRAINER* as an effective and acceptable mHealth app that can reduce pain and psychological disability and has proven acceptable to users in rural communities. These findings are consistent with a Cochrane meta-analysis of RCTs of web-based behavioral interventions for persistent pain that found improvements in pain, impairment, depression, and anxiety.⁵⁵

6.1.2 DOSING AND ADMINISTRATION

All participants are instructed to use the VR program at least once a day and as needed throughout the 8 week study period. Thereafter, the participant can use the program as needed. Section 4.3 provides the justification of dose. PainTRAINER delivers eight sessions via any web-connected platform,

including Android or iOS smartphones, tablets, or personal computers. Patients will complete one session per week in a pre-determined order.

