1.2 SCHEMA

1.3 SCHEDULE OF ACTIVITIES (SOA)

Procedures	Baseline / Screening	Day 1 of Week 1	8-Week Intervention									Post Intervention
	0	1	1	2	3	4	5	6	7	8	9	
Week	0	1	1	2	3	4	5	6	7	8	9	12
Prospective patients identified (Cohort Builder or Provider)	X											
Informed consent in person or over phone	X											
Verify eligibility in chart review or from [name]:	X											
• Medical history												
• Demographics												
Randomization	X											
Baseline Questionnaires (Listed below with)	X											
Shipment of VR device and/or study documents	X											
Technical onboarding call		X										
Milligram Morphine Equivalent (MME) Daily Dose	X										X	
Return of VR Device												X
Deliver honorarium						X					X	X
Self-Reported Questionnaires												
NIH developed baseline demographics, biological sex	X (Day 1)											
Daily Pain Medications Used	X										X	
Daily Pain Intensity	X										X	
Pain Catastrophizing Scale	X (Day 4)		X	X	X	X	X	X	X	X	X	
PROMIS Anxiety Scale	X (Day 4)		X	X	X	X	X	X	X	X	X	
PROMIS Pain Interference Scale	X (Day 4)		X	X	X	X	X	X	X	X	X	
The Pain Self-Efficacy Questionnaire (PSEQ) 2-item short form	X (Day 4)		X	X	X	X	X	X	X	X	X	
Simulator Sickness Questionnaire (VR Only)		X										
Treatment Usage Questionnaire			X	X	X	X	X	X	X	X	X	X
Events Assessment			X	X	X	X	X	X	X	X	X	
Custom Questions		X									X	
Treatment Expectation	X (Day 4)	X										
Concomitant Procedures Questionnaire	X (Day 4)										X	
Primary Pain Questionnaire											X	
Coping with Weekly Pain Questionnaire	X (Day 7)										X	X

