8.3.3 CLASSIFICATION OF AN ADVERSE EVENT

8.3.3.1 SEVERITY OF EVENT

For adverse events (AEs) the following guidelines will be used to describe severity.

- **Mild** – Events require minimal or no treatment and do not interfere with the participant's daily activities.
- **Moderate** – Events result in a low level of inconvenience or concern with the therapeutic measures. Moderate events may cause some interference with functioning.
- **Severe** – Events interrupt a participant's usual daily activity and may require systemic drug therapy or other treatment. Severe events are usually potentially life-threatening or incapacitating. Of note, the term "severe" does not necessarily equate to "serious".

Research staff will call the patient if an event is noted in event assessment that is sent on a biweekly basis. Nothing more than mild to moderate side effects are expected.

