8.3.4 TIME PERIOD AND FREQUENCY FOR EVENT ASSESSMENT AND FOLLOW-UP

The occurrence of an adverse event (AE) or serious adverse event (SAE) may come to the attention of study personnel during review of biweekly event assessments by a study team member as well as on

Day 1. We will employ a general question to allow the patient to provide an event description without bias by presupposing the nature of the event, as follows:

- 1) During the past 14 days, have you experienced anything uncomfortable, distressing or upsetting as a result of using the technology?
 - a. Yes
 - b. No
- 2) If Yes please describe what happened. A research staff member will follow-up with you as soon as possible to learn more.
 - a. [open text]

A designated CRC will review the REDCap dashboard for completed AE assessments on a daily basis throughout the work week. Once they find a completed event assessment form, they will follow-up with a phone call. The following information be obtained from the patient during the call: onset of potential adverse event, event description, when they last used the technology, how long they used the headset, when they stopped using the headset, severity of the potential AE, outcome of the potential AE (see categories, below), time until resolution/stabilization of event, the perceived relationship of the event to the study intervention, whether or not the event was expected (Y/N), whether it was serious.

The outcome can be labeled using one of the following categories:

- Recovered, without treatment
- Recovered, with treatment
- Still Present, no treatment
- Still Present, being treated
- Residual effect(s) present-no treatment
- Residual effect(s) present-being treated

Research staff will record all reportable events with start dates occurring any time after informed consent is obtained until 7 (for non-serious AEs) or 30 days (for SAEs) after the last day of study participation.

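### The event form stops at Week 9 (or Week 8), yet as-needed VR use has no stop date and the SoA places headset return at Week 12

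*Combined protocol and SAP*

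**What the plan says.** - **Permitted use.** Section 6.1.2 asks for at least daily VR use over the eight weeks and then says "Thereafter, the participant can use the program as needed". No end date follows.
- **SoA (1.3).** The row "Events Assessment" is marked at Weeks 1 to 9 and is blank at Week 12. The row "Return of VR Device" has one mark, at Week 12. The row "Treatment Usage Questionnaire" is marked at Weeks 1 to 9 and again at Week 12.
- **Headset return.** Under 5.5, VR participants are "required to return the device after completing the surveys on the 8th week to be eligible for the honorarium". This sets an earliest point for return and no latest one. Section 7.3 also links equipment return to the gift card.
- **Event question.** Section 8.3.4 asks: "During the past 14 days, have you experienced anything uncomfortable, distressing or upsetting as a result of using the technology". It names the biweekly assessments and Day 1 as the occasions when events may come to notice. Section 8.3.3.1 says: "Research staff will call the patient if an event is noted in event assessment that is sent on a biweekly basis".
- **Recording window.** Under 8.3.4, events are recorded "until 7 (for non-serious AEs) or 30 days (for SAEs) after the last day of study participation".
- **Length of participation.** The synopsis gives 12 weeks, and 5.5 describes a 12-week study. Section 4.4 treats a participant as a completer once the Week 8 questionnaire is done.

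**The concern.** At Week 12 the plan asks whether the participant has used the programme, and it allows the headset to be still in the home, but it does not ask whether that use caused any trouble. The event form is the scheduled step that leads to a staff call and an adverse event (AE) record. After the last form, no scheduled item prompts such a report.

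What is at stake is a possible undercount of late VR events such as cybersickness, neck pain or rash. The trial has no separate data and safety monitoring board (10.1.5), and the reviewing IRB's yearly review works from the events that were recorded (10.1.6). Efficacy is not touched, because every primary and secondary endpoint is defined to Week 8.

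**Working it through.** The protocol gives no figure for this interval, so there is none to reproduce. The check is a column count followed by calendar arithmetic.

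**Inputs.** The SoA has 12 columns: Week 0, Day 1 of Week 1, Weeks 1 to 9, and Week 12. Assumption: Week *n* ends on day 7*n*, so Week 8 is day 56, Week 9 is day 63 and Week 12 is day 84.

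**Permitted VR use with no scheduled event question** = day of headset return − day of last event form.

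| Last form | Return | Days |
|---|---|---|
| Week 9 (SoA row) | Week 12 | 84 − 63 = 21 |
| Week 8 (biweekly text in 8.3, or weekly-survey range in 6.4) | Week 12 | 84 − 56 = 28 |
| Either | Soon after the Week 8 surveys | about 0 |

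If the 66-day limit in 4.3 were read as also ending headset use, the figures would be 66 − 63 = 3 and 66 − 56 = 10 days. That section limits completion of the 56-day programme and does not mention later as-needed use. A return later than Week 12 would lengthen the gap.

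**Recording window against the last form.** This depends on when participation ends.

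- *At Week 12 (synopsis, 5.5).* The non-serious window closes on day 84 + 7 = 91. That is 91 − 63 = 28 days after a Week 9 form, or 91 − 56 = 35 after a Week 8 form. The serious-event window closes on day 84 + 30 = 114.
- *At the Week 8 survey (4.4).* The non-serious window closes on day 56 + 7 = 63, the day of the Week 9 form. Recording then does not outrun a Week 9 form, but 6.1.2 still permits VR use after the window has closed.

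On the first reading, events are to be recorded in weeks when no form asks about them. On the second, non-serious events from later permitted use fall outside the recording period. Neither reading provides a scheduled question about use after the last form.

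**Would the present form suffice at Week 12?** Its 14-day recall reaches back to day 84 − 14 = 70. It would miss 70 − 63 = 7 days after a Week 9 form, or 70 − 56 = 14 after a Week 8 form. The recall period therefore has to change on that form.

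**Ceiling on numbers.** Section 9.2 plans 150 participants per arm. At most 150 VR participants are concerned, and a form in both arms adds at most 150 + 150 = 300 short forms. These are start-of-trial ceilings.

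**The case against.** The strongest reply is that the gap may hardly occur. Sections 5.5 and 7.3 tie headset return to payment, and 6.4 makes the month 2 payment by far the largest ($225, against $50 and $25). If return is a condition of that payment, compliant participants have good reason to send the headset back around Week 8 or 9. The text does not say which payment depends on return, so this stands as a reason to treat 21 days as one scenario. It does not remove the gap for anyone who keeps the headset.

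Other channels also remain open. Section 8.2 provides for AE follow-up and questionnaires by support staff, 8.2.1 gives a support telephone number and email, and 6.4 allows calls about equipment return. The item content of the Week 12 questionnaires is not given, so it cannot be excluded that they draw out problem reports. A reader might infer that safety monitoring stops at Week 9, or that events can reach the team only if volunteered. The documents do not support either. What they lack is a scheduled event form.

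A reader might also see a contradiction between 5.5 and the SoA on return. There is none: Week 12 is after the Week 8 surveys. What is missing is a latest date.

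Finally, expected VR events are mostly transient, none are expected with PainTRAINER (8.3.1), and safety analyses are descriptive (9.4.4). All of that stands and limits the weight of the point.

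**Conclusion.** The point holds as a minor gap in scheduled safety questioning. A VR participant who keeps the headset to Week 12 has up to 21 days of permitted use without a scheduled event question, or 28 if the last form is at Week 8. Prompt return brings this near zero. The figures rest on seven-day weeks and return on time at Week 12, and actual use after Week 8 is unknown.

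Two stronger readings should be avoided. The first is that 21 days is the expected gap for the whole VR arm; the payment rule argues against that. The second is that the recording window certainly runs for weeks beyond the last form; that depends on the 12-week reading of participation and does not follow from 4.4. Nor should the benefit of a Week 12 form be stated as a percentage of window days, since calendar days measure neither events nor exposure.

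**What to change.** 1. Add the existing two-item event form to the Week 12 survey. It is needed for the VR arm; using it in both arms is optional, for symmetry.
2. On that form only, ask about the time since the participant's last event form. Leave the 14-day forms unchanged.
3. Tabulate Week 12 reports separately, because the recall period differs.
4. State one latest headset return date, the same in 5.5, 6.1.2 and the SoA.

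The cost is two items on a survey already sent, some follow-up calls, and one amendment that the IRB must approve before use. The downsides are slight extra burden and less exact recall over three to four weeks. The current text is version 6.2, dated October 2023 (10.2), so the change may come late. Week 12 event data would then exist only for participants not yet past Week 12, and the report must say so. If Week 12 follow-up is already complete, the remaining step is to state in the report that scheduled event questioning ended at the last form.
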